6.6.4.3.7. Recurrent Wheeze Events in UK Reconsented Participants

Recurrent wheeze event is defined as two or more protocol-defined wheeze episodes throughout follow-up period. For the participants who have recurrent wheeze events, the end date will be the date of the second protocol-defined wheeze episode.

At the time of Second Year Analysis, incidence of recurrent wheeze events in UK reconsented participants will be summarized by the treatment group. Descriptive statistics will be provided only. Analyses will be performed at the following timepoints:

- Through Day 366 post-dosing/randomization

For participants without medical records retrospectively reviewed after 24 months, the end date will be the start date (date of randomization for participants randomized to no intervention / date of immunization for participants randomized to nirsevimab and treated / date of randomization for participants randomized to nirsevimab but not treated).

For participants with medical records retrospectively reviewed after 24 months and confirmation of no recurrent wheeze events, the end date will be Day 366 or last available date with confirmation of no recurrent wheeze events, whichever is earlier.

Notes:

- If second or subsequent wheeze event occurs after Day 366, it will not be considered and then the end date will be Day 366.
- If a participant receives Beyfortus as part of a routine immunization, any wheeze event occurring after Beyfortus immunization but before Day 366 will not be considered and the end date will be the date of injection of Beyfortus.

- From Day 366 to Day 731 post-dosing/randomization

For participants without medical records retrospectively reviewed after 24 months, the end date will be the start date (date of randomization for participants randomized to no intervention / date of immunization for participants randomized to nirsevimab and

treated / date of randomization for participants randomized to nirsevimab but not treated).

For participants with medical records retrospectively reviewed after 24 months and confirmation of no recurrent wheeze events, the end date will be Day 731 or last available date with confirmation of no recurrent wheeze events, whichever is earlier.

Notes:

- If wheeze events occur before Day 366 or after Day 731, they will not be considered, only wheeze events occurring between Day 366 and Day 731 will be considered.
- If a participant receives Beyfortus as part of a routine immunization, any wheeze event occurring after Beyfortus immunization but before Day 731 will not be considered and the end date will be the date of injection of Beyfortus.

- Through Day 731 post-dosing/randomization

For participants without medical records retrospectively reviewed after 24 months, the end date will be the start date (date of randomization for participants randomized to no intervention / date of immunization for participants randomized to nirsevimab and treated / date of randomization for participants randomized to nirsevimab but not treated).

For participants with medical records retrospectively reviewed after 24 months and confirmation of no recurrent wheeze events, the end date will be Day 731 or last available date with confirmation of no recurrent wheeze events, whichever is earlier.

Notes:

- If second or subsequent wheeze event occurs after Day 731, it will not be considered and then the end date will be Day 731.
- If a participant receives Beyfortus as part of a routine immunization, any wheeze event occurring after Beyfortus immunization will not be considered and the end date will be the date of injection of Beyfortus.

Above analyses will be performed only in UK reconsented participants for which the medical records were retrospectively reviewed after 24 months to determine if medical event(s) meet the definition of wheeze, i.e., “Was retrospective collection of wheeze data performed in participant medical record?” = Yes.

If the number of UK reconsented participants without retrospective collection of wheeze data in participant medical record is superior to 20% of the number of UK reconsented participants, a sensitivity analysis on all UK reconsented participants will be performed.

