8.1.2.4 Wheeze

During the 12- and 24-month follow-up call, the site investigator or staff designee will ask to parents/LARs of UK reconsented participants if the participants had experienced any medically attended cough, chest or breathing problems throughout the study period.

After the 12-month follow-up phone call (when possible) and the 24-month follow-up phone call, the site investigator or staff designee (including third parties authorized by the site investigators) will access the UK reconsented participants' medical record (general practitioner's or hospital's record) to determine if the medical event meets with the definition of wheeze provided by the Sponsor (see below). If so, the event and related complementary information (including any medications prescribed during wheeze) will be retrospectively collected.

For this study, wheeze will be defined as a physician-diagnosed wheeze or asthma or related ear, nose and throat (ENT)/respiratory symptoms at an office visit or an illness for which the child was prescribed medication to treat an ENT/respiratory condition.

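### Recurrent wheeze is analysed only in children whose record was reviewed; if review follows a parent's report, the denominator depends on the outcome, and the 20% fallback is a weak safeguard

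*SAP*

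**What the plan says.** **Ascertainment (Protocol 8.1.2.4, repeated in the synopsis, the schedule of activities and 8.1).** At the 12- and 24-month calls the site "will ask to parents/LARs of UK reconsented participants if the participants had experienced any medically attended cough, chest or breathing problems" over the whole study period. After the call the site "will access the UK reconsented participants' medical record". The stated purpose is "to determine if the medical event meets with the definition of wheeze provided by the Sponsor (see below"). Details are collected if the event qualifies. No sentence says what happens to the record of a child whose parent reports nothing.

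**Analysis set (SAP 6.6.4.3.7).** "Above analyses will be performed only in UK reconsented participants for which the medical records were retrospectively reviewed after 24 months". The set is defined by the eCRF item "Was retrospective collection of wheeze data performed in participant medical record" being answered Yes.

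**Unreviewed children (same section).** "For participants without medical records retrospectively reviewed after 24 months, the end date will be the start date". They are already excluded from the main analysis, so this rule matters only in the fallback.

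**Fallback (same section).** "If the number of UK reconsented participants without retrospective collection of wheeze data in participant medical record is superior to 20" per cent of the UK reconsented total, a sensitivity analysis on all of them is run. The threshold is not stated per arm.

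**Status.** The SAP limits this endpoint to descriptive statistics by group at the Second Year Analysis. Protocol 9.4.3.3 also lists it among endpoints for an efficacy estimate with a 95% CI, for exploratory purposes.

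**The concern.** Membership of the analysis set is decided after randomization, in an open-label trial, by a step that appears to start with what the parent says. If a record is opened mainly when a problem is reported, a child with recurrent wheeze is more likely to be in the denominator than a child without it. Incidence among reviewed children is then too high in both arms. If nirsevimab reduces respiratory illness, it also reduces who is reviewed, so part of any real difference cancels. If parents in the two arms report differently for the same illness, the contrast can move either way, and a difference can appear where none exists.

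At stake are the published wheeze rates and any efficacy figure derived from them under Protocol 9.4.3.3. No confirmatory claim is affected.

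**Working it through.** The documents give no wheeze rate, effect or sample size, so there is no planned figure to reproduce. All rates below are assumptions.

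**Formula.** Let p be the true risk, r the probability of review in a case, and q the probability of review in a non-case.

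- Risk among reviewed = p·r / [p·r + (1 − p)·q]
- Observed RR = true RR × (r nirsevimab / r control) × (share reviewed in control / share reviewed in nirsevimab)

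**1. Equal review probabilities in both arms.** Take p = 0.20 control and 0.15 nirsevimab (RR 0.75), with r = 1.

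| q | Share reviewed, control / nirsevimab | Observed RR |
|---|---|---|
| 1 | 1.00 / 1.00 | 0.750 |
| 0.758 (20% unreviewed overall) | 0.806 / 0.794 | 0.761 |
| 0.4 | 0.52 / 0.49 | 0.796 |
| 0.2 | 0.36 / 0.32 | 0.844 |
| 0 | 0.20 / 0.15 | 1.000 |

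At q = 0.2 the reported risks are 0.20/0.36 = 55.6% and 0.15/0.32 = 46.9%, instead of 20% and 15%. For control risks of 0.10 to 0.30 at q = 0.2, the observed RR is 0.81 to 0.87.

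**2. At the 20% trigger.** With equal reporting and control risk from 0.05 to 0.40, a true RR of 0.75 becomes 0.752 to 0.779, and 0.50 becomes 0.503 to 0.537.

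**3. Unequal reporting (control risk 0.20).**

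| Pattern | Observed RR, true 0.75 | Observed RR, true 1.00 |
|---|---|---|
| Cases reviewed 100% control v 80% nirsevimab; q = 0.3 in both | 0.704 | 0.88 |
| All cases reviewed; non-cases 30% control v 40% nirsevimab | 0.673 | 0.85 |
| All cases reviewed; non-cases 40% control v 30% nirsevimab | 0.963 | 1.18 |

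**4. Does the fallback correct it?** Use the q = 0.2 case, with 24 months of follow-up for non-cases and 12 months on average for cases (assumed). Apply the person-month formula of SAP 6.6.1, also assumed to apply here. An unreviewed child then contributes (0 + 1)/30.4375 = 0.033 month.

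- True rates: 0.20/(0.20×12 + 0.80×24) = 0.20/21.6 and 0.15/(0.15×12 + 0.85×24) = 0.15/22.2, so IRR 0.730.
- Reviewed only: 0.20/(2.4 + 0.16×24) = 0.20/6.24 and 0.15/(1.8 + 0.17×24) = 0.15/5.88, so IRR 0.796.
- All participants: unreviewed children add 0.64×0.033 and 0.68×0.033, so IRR is still 0.796.
- All participants as n/N: 0.15/0.20 = 0.75, the true value.

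The n/N version works only when cases are found equally in both arms. In the first pattern of step 3 it gives (0.15×0.8)/0.20 = 0.60, further from 0.75 than the reviewed-only 0.704.

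**The case against.** **Report-triggered review is not written down.** No condition precedes the access sentence in Protocol 8.1.2.4; the only condition governs collecting an event that qualifies. The SAP provides for reviewed children confirmed free of recurrent wheeze, and its 20% threshold treats non-review as a minority occurrence. A reader might infer that the protocol opens only the records of children with a reported problem. The documents do not support that as a fact. It remains the natural reading, because the event to be checked has no other antecedent than the parent's answer. If every record is opened, this bias disappears, but the plan does not say so.

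**The direction is not fixed.** A reader might infer that a real effect must be pulled toward the null. Step 3 shows otherwise, and Protocol 6.3.2 itself says the direction of open-label bias is uncertain. Figures that erase an effect are easy to choose: true risks of 10% v 8% with 50% v 40% reviewed give 0.10/0.50 = 0.08/0.40 = 20% in both arms. That works only because the ratio of review shares was set equal to the risk ratio. It illustrates the mechanism and estimates nothing.

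**The fallback may suffice.** If review is report-triggered, more than 20% may well be unreviewed, so the fallback would run. SAP 6.1 makes n and % over the analysis population the default, and that form would recover 10% v 8% in the example above. This stands for a proportion. However, the wheeze section defines end dates and SAP 6.6.7.8 summarises wheeze follow-up time, so a rate is also possible, and the section does not say which is meant.

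**The endpoint is descriptive.** True, and it limits the weight of the point. It does not make an inflated incidence correct.

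**Conclusion.** The point holds conditionally. If review follows a parent's report, the reviewed-only denominator depends on the outcome, and incidence is overstated in both arms. With equal review probabilities by case status, a risk ratio of 0.75 is attenuated to about 0.76 when 20% are unreviewed and to 0.84 when only 20% of non-cases are reviewed (control risk 0.20). With unequal open-label reporting the same true ratio came out between 0.67 and 0.96, and a null effect between 0.85 and 1.18. These sizes rest on assumed rates.

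Bias is small when under 20% are unreviewed and reporting is equal. The fallback does not assure either condition. It is conditional, its threshold pools the arms, it leaves the main analysis unchanged, and its follow-up rule leaves a rate where it was. A change is worthwhile but not critical, since nothing confirmatory depends on this endpoint.

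**What to change.** 1. Always present an analysis of all UK reconsented children beside the reviewed-only one, not just above 20%. If review was report-triggered, make the reviewed-only analysis the sensitivity analysis.
2. In the all-reconsented analysis, replace the rule that sets the end date to the start date. A child with a completed 24-month call and no reported problem contributes event-free follow-up to that call. The 24-month answer can carry this alone because it covers the whole study period; requiring the 12-month answer too would fail for families who reconsent after the D366 call, which the schedule of activities allows. A child with a reported problem but no record review, or with neither call nor review, is missing and is handled by imputation or a simple range.
3. Show by arm the numbers asked, reporting a problem and reviewed. State whether records were opened regardless of the parent's answer, and define what Yes means on the eCRF item.

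**Cost.** SAP wording and one derivation, with no new visits. Reported incidence will probably be lower.

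**Downside.** The parent's answer is unblinded and may miss events. It also does not cover the ear, nose and throat part of the wheeze definition, so a no does not exclude a protocol-defined episode. Unequal reporting by arm would still bias the result, which is why the counts in item 3 matter. The documents do not confirm that the answer is stored in the eCRF; if it is not, use n/N over all UK reconsented children and state its limits.

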6.1. General Principles

All data processing, summarization and analyses will be performed using Fortrea's SAS Environment / Version 9.4 (or later) of the SAS® statistical software package.

The default summary statistics for quantitative variables will be the number of observations (n), mean, standard deviation (SD), median, minimum (min) and maximum (max), for those participants with data.

For qualitative variables, the number (n) and percentage (%) of participants with non-missing data per category will be the default summary presentation, and where appropriate and present, the number of missing values as a "Missing" category. Number of participants in the analysis population will be used as denominator for percentages calculation, unless otherwise stated in TFLs mock shell(s).

All statistical comparisons will be made using two sided tests at the $\alpha=0.05$ significance level unless specifically otherwise stated. All null hypotheses will be of no treatment difference. All alternative hypotheses will be two-sided.

Specifications for table, figure and data listing formats can be found in the TFL shells specifications for this study. Please refer to "2. General Format Guidelines" section within TFL shells for more details on presentation of results.

All analyses in the SAP will be carried out for all countries combined and as subgroup analyses by country.

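### The recurrent-wheeze sensitivity analysis ends unreviewed children on Day 1, so it either repeats the main result or imposes one fixed scenario for the missing outcomes

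*SAP*

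**What the plan says.** The event is defined in SAP 6.6.4.3.7: "Recurrent wheeze event is defined as two or more protocol-defined wheeze episodes throughout follow-up period". Protocol 8.1.2.4 has staff ask parents about respiratory problems by telephone and then open the medical record "to determine if the medical event meets with the definition of wheeze provided by the Sponsor". The record is consulted at two times: "After the 12-month follow-up phone call (when possible) and the 24-month follow-up phone call".

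On who is analysed, SAP 6.6.4.3.7 says: "Above analyses will be performed only in UK reconsented participants for which the medical records were retrospectively reviewed after 24 months". The trigger for the sensitivity analysis is a count of children "without retrospective collection of wheeze data in participant medical record is superior to 20% of the number of UK reconsented participants". When it is met, the plan is that "a sensitivity analysis on all UK reconsented participants will be performed". No method is given for it.

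The same rule for children without review appears under all three time windows (to Day 366, Day 366 to 731, to Day 731): "For participants without medical records retrospectively reviewed after 24 months, the end date will be the start date". The start date is randomization, or immunization for treated nirsevimab children.

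On percentages, SAP 6.1 gives a default: "Number of participants in the analysis population will be used as denominator for percentages calculation". It allows exceptions in the table shells and a separate category for missing values.

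**The concern.** A sensitivity analysis for missing outcomes should show how far the result could move under other assumptions about the children who were not observed. This one runs only when more than a fifth of outcomes are already unobserved. Because the main analysis excludes unreviewed children, the Day 1 end-date rule can affect the incidence comparison only here. It is therefore the working specification of the sensitivity analysis.

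The SAP has an imputation plan for the primary endpoint (6.6.2.2) and both key secondary endpoints (6.6.5.1.2 and 6.6.5.2.2), but none for wheeze status. SAP 5.2.3.4 covers only missing wheeze dates.

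Unequal missingness is a risk the documents already recognise. SAP 6.6.2.2 anticipates more withdrawals in the no-intervention arm because the study is open-label, and Protocol 6.3.2 accepts that the two groups may not receive equal attention. At stake is whether readers of the Second Year Analysis can judge how robust the wheeze comparison is.

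**Working it through.** The documents give no expected rate, event count or power for recurrent wheeze, so there is no planned figure to reproduce. The check applies the SAP's own rules.

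**Inputs from the documents.** Person-months = (end − start + 1)/30.4375 (SAP 6.6.1). End = start for unreviewed children (SAP 6.6.4.3.7). The trigger is more than 20% unreviewed, pooled over arms.

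**Assumptions, not from the documents.** Equal arms, 20% recurrent wheeze among reviewed children in both arms, events at mid follow-up, and the unreviewed shares shown below.

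**Person-time contributed.**
- Unreviewed child: 1/30.4375 = 0.033 person-months.
- Event-free child followed to Day 731: 731/30.4375 = 24.02 person-months.
- Ratio: 0.033/24.02, about 0.14%.

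**Incidence as a rate.** Mean person-time per reviewed child is 0.80 × 24.02 + 0.20 × 12.01 = 21.61 months, so the main-analysis rate is 0.20/21.61 = 0.00925 per month. With 21% unreviewed, the sensitivity rate is (0.79 × 0.20)/(0.79 × 21.61 + 0.21 × 0.033), which is lower by 0.04%. With 40% unreviewed it is lower by 0.10%. With 30% unreviewed in control and 15% in nirsevimab, the rate ratio moves from 1.0000 to 1.0004. The main analysis is repeated.

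**Incidence as a percentage of all reconsented children, with no recorded event counted as no event.** The reviewed percentage is multiplied by (1 − unreviewed share).
- 21% unreviewed: 20% × 0.79 = 15.8%.
- 40% unreviewed: 20% × 0.60 = 12.0%.

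The risk ratio is multiplied by (1 − share in nirsevimab)/(1 − share in control). With no true effect:

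| Unreviewed, control | Unreviewed, nirsevimab | Ratio, nirsevimab to control |
|---|---|---|
| 21% | 21% | 0.79/0.79 = 1.00 |
| 30% | 20% | 0.80/0.70 = 1.14 |
| 20% | 30% | 0.70/0.80 = 0.88 |

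The unequal splits average 25%, so both would trigger the analysis. The shift reflects only the difference in missing shares.

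**Day 366 to Day 731 window.** An end date of Day 1 precedes the opening of the window. If follow-up starts at Day 366, the formula gives (1 − 366 + 1)/30.4375 = −11.96 person-months. If it starts at Day 1, the single day lies outside the window. Neither is usable.

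**What varying the missing outcomes would show.** Take 21% unreviewed per arm and 20% wheeze among reviewed children in both arms. If no unreviewed child has recurrent wheeze, an arm's incidence is 0.79 × 0.20 = 0.158. If all do, it is 0.158 + 0.21 = 0.368. The risk ratio then lies between 0.158/0.368 = 0.43 and 0.368/0.158 = 2.33. The planned analysis returns 1.00 in this setting, whichever way incidence is expressed.

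**The case against.** Five points can be made for the plan.

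1. A reader might infer that the SAP scores every unreviewed child as wheeze-free. It does not say so. SAP 6.6.4.3.7 sets only an end date. The SAP 6.1 denominator is a default that the table shells, which are not available here, may override, and unreviewed children could be shown as missing. A child reviewed after 12 months but not after 24 could also have recorded episodes; the SAP does not say whether the second-episode end date or the Day 1 end date then applies. This stands, and it is why both forms of incidence are worked through above.

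2. A reader might infer that incidence is understated by more than 20%. That holds only if unreviewed children wheeze as often as reviewed ones. Protocol 8.1.2.4 can be read as review prompted by a parent's report. If so, some unreviewed children had nothing to report, and a denominator of all participants would be closer to the truth. The text is ambiguous, so no such figure is claimed. The Day 1 end date fits that reading poorly for a rate, because it discards the follow-up of true non-cases.

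3. The percentage form does change an assumption: it moves from reviewed children only to missing counted as no event, which is a legitimate lower bound for each arm's incidence. This stands. The criticism is that it is one fixed scenario, applied alike to both arms, and does not bound the comparison.

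4. The unequal splits are invented and could run either way. This also stands; no direction of bias is claimed.

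5. The analysis is contingent and descriptive. That limits the consequence but does not repair the rule.

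**Conclusion.** The point holds as a fault in a stated rule. Under a person-time rate the planned check cannot differ materially from the main analysis: at most 0.10% in the rate with up to 40% unreviewed, under the stated assumptions. Under a percentage it gives one fixed scenario whose effect on the arm comparison depends only on how review completeness differs between arms (1.14 or 0.88 in the two assumed splits, 1.00 if equal). In the Day 366 to Day 731 window the rule is unusable whatever is assumed.

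The estimator is also open. Protocol 9.4.3.3 lists recurrent wheeze among the exact-method efficacy analyses, while SAP 6.6.4.3.7 plans descriptive statistics only and SAP 6.6.7.8 summarises follow-up time for this endpoint.

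Recurrent wheeze is secondary and descriptive, and no confirmatory conclusion depends on it. The change should still be made, because the analysis as written could be mistaken for evidence of robustness.

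**What to change.** In SAP 6.6.4.3.7:

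- Treat children without record review as having missing wheeze status, and delete the Day 1 end-date rule in all three windows.
- State whether incidence is a percentage or a person-time rate, and when follow-up starts in the Day 366 to Day 731 window.
- Say how a child reviewed after 12 months but not after 24 is handled.
- Report the number and share of unreviewed children by arm.
- Replace the triggered analysis with bounds by arm (none, then all, of the unreviewed children with recurrent wheeze, including the opposing combinations), or with the tipping-point grid already specified in SAP 6.6.2.2.

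Multiple imputation is optional. If used, it should draw only on variables confirmed to be in the database; the documents do not show that parents' negative answers at the 12- and 24-month calls are recorded in the eCRF.

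The cost is a little extra programming and wider reported uncertainty. Neither the bounds nor the grid needs new data.
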